## **7.2.2 Reporting of Pregnancy and Lactation to the Sponsor and to Merck**

Although pregnancy and lactation are not considered adverse events, it is the responsibility of investigators or their designees to report any pregnancy or lactation in a subject (spontaneously reported to them) that occurs during the trial.

Pregnancies and lactations that occur after the consent form is signed but before treatment allocation/randomization must be reported by the investigator if they cause the subject to be excluded from the trial, or are the result of a protocol-specified intervention, including but not limited to washout or discontinuation of usual therapy, diet, placebo treatment or a procedure.

Pregnancies and lactations that occur from the time of treatment allocation/randomization through 120 days following cessation of Sponsor's product, or 30 days following cessation of treatment if the subject initiates new anticancer therapy, whichever is earlier, must be reported by the investigator. All reported pregnancies must be followed to the completion/termination of the pregnancy. Pregnancy outcomes of spontaneous abortion, missed abortion, benign hydatidiform mole, blighted ovum, fetal death, intrauterine death, miscarriage and stillbirth must be reported as serious events (Important Medical Events). If the pregnancy continues to term, the outcome (health of infant) must also be reported.

Such events must be reported within 24 hours to the Sponsor and within 2 working days to Merck Global Safety. (Attn: Worldwide Product Safety; [contact])

## **7.2.3 Immediate Reporting of Adverse Events to the Sponsor and to Merck**

### **7.2.3.1 Serious Adverse Events**

An SAE is any AE that fulfills one of the criteria outlined in **Table 6**.

Examples of such "important medical events" include allergic bronchospasm requiring intensive treatment in an emergency room or at home, blood dyscrasias or convulsions that do not result in inpatient hospitalization, or the development of drug dependency or drug abuse.

Medical and scientific judgment should be exercised in deciding whether expedited reporting is appropriate in other situations, such as with important medical events described above.

Events that meet SAE criteria must be recorded and reported regardless of expectedness or assessed association with study drug.

**Note:** Planned hospital admissions or surgical procedures for elective procedures or for an illness or disease that existed before the signing of the ICF or before the subject was enrolled in the study will not be captured as SAEs. If planned admissions or procedures occur at a

time other than what was planned (i.e., due to an exacerbation in the preexisting illness or disease), they should be reported as SAEs.

For the time period beginning when study drugs (FMT and pembrolizumab combination on day +1) are administered, any serious adverse event, or follow up to a serious adverse event, including death due to any cause other than progression of the cancer under study (reference Section 7.2.3.3 for additional details) that occurs to any subject must be reported within 24 hours to the Principal Investigator and within 2 working days to Merck Global Safety if it causes the subject to be excluded from the trial, or is the result of a protocol-specified intervention, including but not limited to washout or discontinuation of usual therapy, diet, placebo treatment or a procedure.

For the time period beginning study drugs (FMT and pembrolizumab combination on day +1) are administered through 90 days following cessation of treatment, or 30 days following cessation of treatment if the subject initiates new anticancer therapy, whichever is earlier, any serious adverse event, or follow up to a serious adverse event, including death due to any cause other than progression of the cancer under study (reference Section 7.2.3.3 for additional details), whether or not related to the pembrolizumab and/or FMT, must be reported within 24 hours to the Principal Investigator and within 2 working days to Merck Global Safety.

Additionally, any serious adverse event, considered by an investigator to be related to pembrolizumab and/or FMT that is brought to the attention of the investigator at any time following C1D1 through the end of the specified safety follow-up period specified in the paragraph above, or at any time outside of the time period specified in the previous paragraph also must be reported immediately to the Principal Investigator and to Merck Global Safety.

All subjects with serious adverse events must be followed up for outcome.

The causal relationship to study drugs is determined by a physician and should be used to assess all adverse events (AE). The causal relationship can be one of the following:

- Unrelated:
  - Exposure to investigational agents (FMT and/or pembrolizumab) has not occurred; *or*
  - Administration of investigational agents (FMT and/or pembrolizumab) and occurrence of AE are not reasonably related in time; *or*
  - AE is considered likely to be related to an etiology other than the use of the investigational agents (FMT and/or pembrolizumab); and there are no facts or arguments to suggest a causal relationship to the investigational agents (FMT and/or pembrolizumab).
- Possibly related:
  - Administration of the investigational agents (FMT and/or pembrolizumab) are reasonably related in time; *and*

- AE could not be explained equally well by factors or causes other than exposure to investigational agents (FMT and/or pembrolizumab).
- Probably related:
  - Administration of investigational agents (FMT and/or pembrolizumab) and occurrence of AE are reasonably related in time; *and*
  - AE is more likely explained by exposure to the investigational agents (FMT and/or pembrolizumab) than by other factors or causes.

Every effort should be made to discern whether any reported AE/SAE are related to either pembrolizumab or FMT. If it is deemed equally likely for AE/SAE to be related to both, that should be reflected as well.

**SAE reports and any other relevant safety information are to be forwarded to the Merck Global Safety [contact]**

A copy of all 15 Day Reports and Annual Progress Reports is submitted as required by FDA, European Union (EU), Pharmaceutical and Medical Devices agency (PMDA) or other local regulators. Investigators will cross reference this submission according to local regulations to the Merck Investigational Compound Number (IND, CSA, etc.) at the time of submission. Additionally investigators will submit a copy of these reports to Merck & Co., Inc. (Attn: Worldwide Product Safety; [contact]) at the time of submission to FDA.

### **7.2.3.2 Events of Clinical Interest**

Selected non-serious and serious adverse events are also known as Events of Clinical Interest (ECI) and must be reported within 24 hours to the Sponsor and within 2 working days to Merck Global Safety. (Attn: Worldwide Product Safety; [contact]).

For the time period beginning when the consent form is signed until treatment allocation/randomization, any ECI, or follow up to an ECI, that occurs to any subject must be reported within 24 hours to the Sponsor and within 2 working days to Merck Global Safety if it causes the subject to be excluded from the trial, or is the result of a protocol-specified intervention, including but not limited to washout or discontinuation of usual therapy, diet, placebo treatment or a procedure.

For the time period beginning at treatment allocation/randomization through 90 days following cessation of treatment, or 30 days following cessation of treatment if the subject initiates new anticancer therapy, whichever is earlier, any ECI, or follow up to an ECI, whether or not related to pembrolizumab, must be reported within 24 hours to the Sponsor and within 24 hours to Merck Global Safety.

Events of clinical interest for this trial include:

1. Any use of oral and/or intravenous antibiotics for any duration/indication must be reported within 24 hours to the Principal Investigator. Reporting should include the name, dose and duration of antibiotic prescribed and the indication(s) it was prescribed for.

2. Any use of oral and/or intravenous steroids for any duration/indication must be reported within 24 hours to the Principal Investigator. Reporting should include the name, dose and duration of steroid prescribed and the indication(s) it was prescribed for.
3. An overdose of pembrolizumab and/or FMT, as defined in Section 7.2.1 - Definition of an Overdose for This Protocol and Reporting of Overdose to the Principal Investigator, that is not associated with clinical symptoms or abnormal laboratory results.
4. An elevated AST or ALT lab value that is greater than or equal to 3X the upper limit of normal and an elevated total bilirubin lab value that is greater than or equal to 2X the upper limit of normal and, at the same time, an alkaline phosphatase lab value that is less than 2X the upper limit of normal, as determined by way of protocol-specified laboratory testing or unscheduled laboratory testing.\*

\*Note: These criteria are based upon available regulatory guidance documents. The purpose of the criteria is to specify a threshold of abnormal hepatic tests that may require an additional evaluation for an underlying etiology.

### **7.2.3.3 Protocol-Specific Exceptions to Serious Adverse Event Reporting**

Suspected/actual events as outlined in this section will not be reported to Merck as described in Section 7.2.3.- Immediate Reporting of Adverse Events to the Sponsor and to Merck, unless there is evidence suggesting a causal relationship between the drug and the event. Any such event will be submitted to the Principal Investigator within 24 hours and to Merck Global Safety within 2 working days either by electronic or paper media.

Specifically, the suspected/actual events covered in this exception include any event that is disease progression of the cancer under study.

The Principal Investigator will monitor unblinded aggregated efficacy endpoint events and safety data to ensure the safety of the subjects in the trial. Any suspected endpoint which upon review is not progression of the cancer under study will be forwarded to Merck Global Safety as a SAE within 2 working days of determination that the event is not progression of the cancer under study

Hospitalization related to convenience (e.g. transportation issues etc.) will not be considered a SAE.

### **7.2.4 Evaluating Adverse Events**

An investigator who is a qualified physician will evaluate all adverse events according to the NCI Common Terminology for Adverse Events (CTCAE), version 5.0. Any adverse event which changes CTCAE grade over the course of a given episode will have each change of grade recorded on the adverse event case report forms/worksheets.

All adverse events regardless of CTCAE grade must also be evaluated for seriousness and attribution to pembrolizumab and/or FMT.

**Table 7.2.4-1 Evaluating Adverse Events**

An investigator who is a qualified physician or qualified designee, will evaluate all adverse events as to:

V5.0 CTCAE Grading	Grade 1	Mild; asymptomatic or mild symptoms; clinical or diagnostic observations only; intervention not indicated.
	Grade 2	Moderate; minimal, local or noninvasive intervention indicated; limiting age-appropriate instrumental ADL.
	Grade 3	Severe or medically significant but not immediately life-threatening; hospitalization or prolongation of hospitalization indicated; disabling; limiting self-care ADL.
	Grade 4	Life threatening consequences; urgent intervention indicated.
	Grade 5	Death related to AE
Seriousness	A serious adverse event is any adverse event occurring at any dose or during any use of pembrolizumab and/or FMT that:	
	† Results in death ; or	
	† Is life threatening ; or places the subject, in the view of the investigator, at immediate risk of death from the event as it occurred (Note: This does not include an adverse event that, had it occurred in a more severe form, might have caused death.); or	
	† Results in a persistent or significant disability/incapacity (substantial disruption of one’s ability to conduct normal life functions); or	
	† Results in or prolongs an existing inpatient hospitalization (hospitalization is defined as an inpatient admission, regardless of length of stay, even if the hospitalization is a precautionary measure for continued observation. (Note: Hospitalization for an elective procedure to treat a pre-existing condition that has not worsened is not a serious adverse event. A pre-existing condition is a clinical condition that is diagnosed prior to the use of a pembrolizumab and is documented in the patient’s medical history.); or	
	† Is a congenital anomaly/birth defect (in offspring of subject taking the product regardless of time to diagnosis); or	
	Is a new cancer (that is not a condition of the study) (although not serious per ICH definition, is reportable to the Sponsor within 24 hours and to Merck within 2 working days to meet certain local requirements); or	
	Is an overdose (whether accidental or intentional). Any adverse event associated with an overdose is considered a serious adverse event for collection purposes. An overdose that is not associated with an adverse event is considered a non-serious event of clinical interest and must be reported within 24 hours to the Sponsor and to Merck within 2 working days..	
Other important medical events that may not result in death, not be life threatening, or not require hospitalization may be considered a serious adverse event when, based upon appropriate medical judgment, the event may jeopardize the subject and may require medical or surgical intervention to prevent one of the outcomes		

	listed previously (designated above by a †).	
Duration	Record the start and stop dates of the adverse event. If less than 1 day, indicate the appropriate length of time and units	
Action taken	Did the adverse event cause pembrolizumab and/or FMT to be discontinued?	
Relationship to pembrolizumab	Did pembrolizumab and/or FMT cause the adverse event? The determination of the likelihood that pembrolizumab and/or FMT caused the adverse event will be provided by an investigator who is a qualified physician. The investigator's signed/dated initials on the source document or worksheet that supports the causality noted on the AE form, ensures that a medically qualified assessment of causality was done. This initialed document must be retained for the required regulatory time frame. The criteria below are intended as reference guidelines to assist the investigator in assessing the likelihood of a relationship between the test drug and the adverse event based upon the available information.  The following components are to be used to assess the relationship between pembrolizumab and/or FMT and the AE; the greater the correlation with the components and their respective elements (in number and/or intensity), the more likely pembrolizumab and/or FMT caused the adverse event (AE):	
	Exposure	Is there evidence that the subject was actually exposed to pembrolizumab and/or FMT such as: reliable history, acceptable compliance assessment (pill count, diary, etc.), expected pharmacologic effect, or measurement of drug/metabolite in bodily specimen?
	Time Course	Did the AE follow in a reasonable temporal sequence from administration of pembrolizumab and/or FMT? Is the time of onset of the AE compatible with a drug-induced effect (applies to trials with investigational medicinal product)?
	Likely Cause	Is the AE not reasonably explained by another etiology such as underlying disease, other drug(s)/vaccine(s), or other host or environmental factors

Relationship to pembrolizumab and/or FMT (continued)	The following components are to be used to assess the relationship between the test drug and the AE: (continued)	
	Dechallenge	
Was pembrolizumab discontinued or dose/exposure/frequency reduced?
 
If yes, did the AE resolve or improve?
 
If yes, this is a positive dechallenge. If no, this is a negative dechallenge.
 
(Note: This criterion is not applicable if: (1) the AE resulted in death or permanent disability; (2) the AE resolved/improved despite continuation of the Sponsor's product; or (3) the trial is a single-dose drug trial); or (4) Sponsor's product(s) is/are only used one time.)

	Rechallenge	
Was the subject re-exposed to pembrolizumab in this study?
 
If yes, did the AE recur or worsen?
 
If yes, this is a positive rechallenge. If no, this is a negative rechallenge.
 
(Note: This criterion is not applicable if: (1) the initial AE resulted in death or permanent disability, or (2) the trial is a single-dose drug trial); or (3) Sponsor's product(s) is/are used only one time).
 
NOTE: IF A RECHALLENGE IS PLANNED FOR AN ADVERSE EVENT WHICH WAS SERIOUS AND WHICH MAY HAVE BEEN CAUSED BY pembrolizumab , OR IF REEXPOSURE TO pembrolizumab POSES ADDITIONAL POTENTIAL SIGNIFICANT RISK TO THE SUBJECT, THEN THE RECHALLENGE MUST BE APPROVED IN ADVANCE BY THE SPONSOR AS PER DOSE MODIFICATION GUIDELINES IN THE PROTOCOL.

	Consistency with Trial Treatment Profile	Is the clinical/pathological presentation of the AE consistent with previous knowledge regarding pembrolizumab or drug class pharmacology or toxicology?
The assessment of relationship will be reported on the case report forms /worksheets by an investigator who is a qualified physician according to his/her best clinical judgment, including consideration of the above elements.		
Record one of the following	Use the following scale of criteria as guidance (not all criteria must be present to be indicative of pembrolizumab and/or FMT relationship).	
Yes, there is a reasonable possibility of pembrolizumab and/or FMT relationship.	There is evidence of exposure to pembrolizumab and/or FMT. The temporal sequence of the AE onset relative to the administration of pembrolizumab is reasonable. The AE is more likely explained by pembrolizumab than by another cause.	
No, there is not a reasonable possibility of pembrolizumab and/or FMT relationship	Subject did not receive the pembrolizumab and/or FMT OR temporal sequence of the AE onset relative to administration of pembrolizumab is not reasonable OR the AE is more likely explained by another cause than the pembrolizumab . (Also entered for a subject with overdose without an	

	associated AE.)
--	-----------------

### **7.2.5 Sponsor Responsibility for Reporting Adverse Events**

All Adverse Events will be reported to regulatory authorities, IRB/IECs and investigators in accordance with all applicable global laws and regulations.

## **8.0 STATISTICAL ANALYSIS PLAN**

### **8.1. Overview of the Study**

This study is designed to assess the objective response rate (ORR) and toxicity of the addition of FMT to PD-1/PD-L1 treated patients. The patients will be evaluated for response and toxicity using the Simon's two-stage phase II design.

### **8.2. Sample Size**

13 patients will be accrued in the first stage. If the study continues to the second stage, an additional 7 patients will be accrued. The detailed decision rule and sample size justification are in the following Section 8.5.1.

### **8.3. Dose Limiting Toxicity (DLT) Definition and Monitoring**

Dose limiting toxicity (DLT) will be defined based on incidence of AEs considered **possibly related** to pembrolizumab and/or FMT that occur any time from the initial dose of study treatment of FMT in combination with pembrolizumab, with severity graded according to the NCI Common Terminology Criteria for Adverse Events (CTCAE), Version 5.0. Any occurrence of CTCAE grade 3 or greater adverse event in four weeks following the administration of the FMT will be considered a DLT.

DLT will be monitored during DLT monitoring period, latter defined as 4-week period following administration of FMT/pembrolizumab. During DLT monitoring period, no further patient enrollment will occur. DLTs will be monitored for the first 3 patients in each cohort. During the DLT monitoring period, only 1 patient will be enrolled per month.

Given that this is a novel combination study, in the event of AE, treating investigator(s) will make every effort to attribute AE to either pembrolizumab or FMT. In the event that AE attribution is "possibly" related to both pembrolizumab or FMT, this will be reflected in the AE attribution form.

### **8.4. Stopping Criteria**

Occurrence of any death occurring within 30 days of receiving the investigational agent that is considered at least possibly related to the agent will be treated as a study stopping criterion.

During this period of time, the study investigators and independent DSMB will evaluate death to determine causality (relationship to either pembrolizumab or FMT or both). Autopsies will be encouraged.

Study will not recur till after 30 day period has passed. Study will only resume if study investigators and independent DSMB collectively determine that death was unlikely related to investigational agents (FMT and/or pembrolizumab).

## **8.5. Analysis Plan**

### **8.5.1. Decision Rule and Sample Size Justification**

#### **8.5.1.1. Patient Evaluability and Definition of Objective Response**

All patients meeting the eligibility criteria who have signed a consent form and begun pembrolizumab and/or FMT will be considered evaluable for estimation of the response probability. For evaluable patients, objective response will be assessed by RECIST 1.1.

#### **8.5.1.2. Decision Rule:**

Based on prior data on response rates in this patient population, the largest ORR where the proposed treatment would be considered unpromising in this population is 5%. The smallest success proportion that would warrant further subsequent studies with the proposed treatment in this patient population is 25%. The following design is based on Simon's minimax two-stage study design and uses to test the null hypothesis that the true success rate in each patient population is at most 5%.

In Stage 1: Enter 13 evaluable patients and follow for at least 12 weeks. If 0 patients have a confirmed response in this timeframe, we will consider this early evidence that this treatment regimen is not sufficiently active in this patient population. If 1 or more patients have a response, then accrual will continue in the second stage of this trial.

In Stage 2: Enter an additional 7 evaluable patients to the trial. If 2 or fewer successes are observed in the 20 evaluable patients, we will consider this sufficient evidence that this treatment is not sufficiently effective in this patient population. If 3 or more successes are observed in the first 20 evaluable patients, then this treatment will be considered promising in this patient population and will be evaluated further in future studies.

Power and Significance Level: Assuming that the number of successes is binomially distributed, this decision rule has a significance level of 0.07; i.e., there is a 7% chance of finding the drug to be effective when it truly is not. This decision rule has 90% power to detect an effective treatment given that the true response rate is at least 25% using this treatment.

### **8.5.3. Analysis of Secondary and Exploratory Endpoints**

The secondary objective is to investigate how FMT administration affects composition and function of T-cells and innate/adaptive immune system subsets. The pre-post difference of these endpoints will be compared between responders and non-responders with the two sided t-test or Wilcoxon rank sum test where appropriate. The exploratory objective is to determine whether PD-1 response in responding patients is associated with common gut microbiota profile. The same statistical analysis methods will be used as for the secondary endpoints.

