### 3.2 Secondary Objective(s) & Hypothesis(es)

- (1) **Objective:** To investigate how FMT administration affects composition and function of T-cells and innate/adaptive immune system subsets.

**Hypothesis:** PD-1 responder-derived FMT augments tumor antigen-specific CD8+ and CD4+ T-cell responses, DC maturation/function and innate immune responses to melanoma.

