### 4.2.4.2 Biomarker Research

Biomarker endpoints include:

Analysis of bacterial taxa occurrence (within-sample and between-sample differences) in PD-1 responders, FMT responders and FMT non-responders.

Evaluation of anti-tumor T-cell responses, DC function/maturity by multi-parameter flow cytometry, multiplex immunohistochemistry, analysis of T-cell receptor (TCR) clonality/diversity and genetic mutation/expression studies (RNAseq, exome sequencing).

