#### **7.1.2.6 Tumor Imaging and Assessment of Disease**

On this study, response will be first assessed after FMT administration and 4 cycles of pembrolizumab (cycle 4; week 21-22) and after cycle 8 (week 33-34). Assessment of antitumor response will be based on RECIST 1.1. Because tumor pseudo-progression is a well-recognized consequence of PD-1 based immunotherapies **and use of FMT as a therapeutic agent in cancer is highly novel**, confirmation of PD requires continued presence of PD on 2 consecutive assessments of response done at least 4 weeks apart during which pembrolizumab will be continued.

Computed tomography (CT) of chest, abdomen, pelvis and CT/MRI brain scans (if clinically indicated) will be performed at screening and after cycle 4 (Day 1  $\pm$  7 days). Following cycle 4, reimaging will occur every 4 cycles (12 weeks) starting with cycle 8 (cycles 12, 16, 20 etc.).

PD documented at any evaluation time point **will be followed** with a repeated radiographic evaluation at the Principal Investigator's discretion to rule out tumor pseudo-progression.

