### **11.2 Correlative Studies**

Correlative studies will be performed using PBMCs and tumor tissues collected from the patients included in the study as detailed in the laboratory manual.

These studies will include:

- Multiparameter flow cytometry to evaluate T cell phenotype and function
- Nanosorting studies of tumor biopsies
- RNAseq and exome sequencing
- Studies of T cell repertoire
- Stool samples will be used for genomic evaluation of microbiota
  - 16S ribosomal RNA (rRNA) and metagenomic sequencing will be used to characterize the complexity of the human microbiome in the stool and at multiple body sites. 16S rRNA gene sequencing is a well-established method for studying phylogeny and taxonomy of samples from complex microbiomes or environments that are difficult or impossible to study.

Prior biopsy samples including primary tumor shave/excision biopsies, sentinel lymph node biopsies, completion lymph node dissection samples will be requested from pathology. Prior tissue obtained to establish metastatic disease, as part of definitive surgical management or as part of standard of care testing prior to current therapy will also be requested. These samples will be used for immunohistochemical (IHC) and RNA sequencing studies to evaluate immune responses and gene signatures associated with improved clinical outcome.

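### The secondary objective asks how FMT affects immune subsets, but the only planned analysis contrasts responders with non-responders; no all-patient estimate of change is planned

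*Combined protocol and SAP*

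**What the plan says.** Section 8.5.3 restates the objective: "The secondary objective is to investigate how FMT administration affects composition and function of T-cells and innate/adaptive immune system subsets". The hypothesis in section 3.2 is directional and makes no reference to response status: "PD-1 responder-derived FMT augments tumor antigen-specific CD8+ and CD4+ T-cell responses, DC maturation/function and innate immune responses to melanoma".

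The analysis in section 8.5.3 is a single sentence: "The pre-post difference of these endpoints will be compared between responders and non-responders with the two sided t-test or Wilcoxon rank sum test", the choice of test depending on which is appropriate. The same methods are carried over to the exploratory microbiota objective. The sentence gives no alpha and does not say which post-treatment sample is meant.

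The other places where an all-patient analysis might be found do not contain one:
- Section 4.2.4.2 lists assays ("Evaluation of anti-tumor T-cell responses, DC function/maturity by multi-parameter flow cytometry, multiplex immunohistochemistry").
- Section 11.2 also lists assays ("Multiparameter flow cytometry to evaluate T cell phenotype and function"). It refers to a laboratory manual for the studies; section 8.5.3 does not refer to that manual for analysis.
- Section 8.5.2 plans overall summaries only for ORR and toxicity.
- The study calendar notes and section 7.1.2.7 give sampling times: blood at screening and in each of cycles 1 to 8, and biopsies at screening and on treatment.

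The stage 1 rule in section 8.5.1.2 reads: "If 0 patients have a confirmed response in this timeframe", the regimen is taken as not sufficiently active. At least one response among 13 lets accrual continue to 20, and 3 or more of 20 is promising.

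**The concern.** The objective and hypothesis concern change in treated patients. The planned test concerns the difference in change between two subgroups defined by outcome. These are different estimands. If an immune measure rose by the same amount in responders and non-responders, the hypothesis would be supported, yet the planned test would be expected to show no difference.

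The contrast also depends on the responder count, which the design expects to be small. It is weakest, or cannot be made at all, when the treatment is inactive. In that case it would be informative to know whether immune change occurred without clinical response.

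At stake is the interpretation of the secondary objective, not the primary decision.

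**Working it through.** **Inputs.** From section 8.5.1.2: stage 1 n = 13 (stop at 0), stage 2 n = 7, promising at 3 or more of 20, null ORR 5%, target ORR 25%, stated significance level 0.07 and power 90%. Assumed, because the documents give no value for the secondary analysis: two-sided alpha 0.05, normally distributed change, and results expressed in SDs of the change.

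**1. The plan's own figures.** P(promising) = Σ over x = 1 to 13 of P(X1 = x) · P(X2 ≥ 3 − x), with X1 ~ Bin(13, p) and X2 ~ Bin(7, p). This gives 0.0736 at p = 0.05 and 0.903 at p = 0.25, matching the stated 0.07 and 90%. The design figures are not in question.

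**2. How often responders are absent or nearly so.**
- Stop at 0/13: 0.95^13 = 0.513; 0.75^13 = 0.024.
- Exactly one responder of 20 under the rule (one of 13, then none of 7): 13 · p · (1 − p)^19 = 0.245 at 5% and 0.014 at 25%. With 1 versus 19, the smallest attainable two-sided exact rank-sum p-value is 2/20 = 0.10.

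**3. The stop probability is not exactly the probability of no comparison.** It can move either way:
- Later responses lower it. With an assumed chance q of a later response per patient, ((1 − p)(1 − q))^13 at p = 0.05 is 0.450 for q = 1% and 0.264 for q = 5%. At p = 0.25 it is 0.021 and 0.012.
- Missing responder pairs raise it. At p = 0.05 with no later responses, if a sole responder lacks a pair with an assumed 10% to 30% chance, the probability is at least 0.513 + 0.10 · 0.245 = 0.538 to 0.513 + 0.30 · 0.245 = 0.587.

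**4. Precision of the planned contrast.** Noncentral t with 18 df and noncentrality d · √(n1·n2/(n1 + n2)); difference d for 80% power:
- 3 versus 17 (smallest promising result): d = 1.86 SD.
- 5 versus 15 (expected count at 25%): d = 1.53 SD.

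The 95% CI half-width is t(0.975, 18) · √(1/n1 + 1/n2): 2.16 SD at 1 versus 19, 1.32 SD at 3 versus 17, and 1.08 SD at 5 versus 15.

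**5. Precision of an all-patient mean change.** The half-width is t(0.975, n − 1)/√n: 0.47 SD with 20 pairs, 0.60 SD with 13, and 0.72 SD with 10.

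**6. Illustration at 5 versus 15, SD 1 (simulated).**
- All patients change by 1 SD: the planned t-test rejects in about 5% of trials, and the all-patient 95% CI excludes zero in about 99%.
- Only responders change (1.5 versus 0 SD): about 78% and 23%.

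The first result follows from the form of the test. The second shows that the all-patient estimate cannot replace the contrast.

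**The case against.** The strongest reply is that the responder contrast is deliberate. Section 4.2.1 proposes converting non-responders into responders with evidence of anti-melanoma T-cell responses, and section 4.2.4.2 separates FMT responders from FMT non-responders for the microbiota. Linking immune change to response fits that aim. This stands, and it is why the contrast should stay.

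A second reply is that one arm cannot isolate FMT, so an all-patient estimate does not answer the stated objective in full. This also stands. It applies equally to the responder contrast, and it governs how the result is worded.

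Three stronger readings are tempting, and the documents do not support them:
- A reader might infer that a stage 1 stop leaves the secondary objective with no result. Section 8.5.3 already implies a pre-post difference for each patient, so the quantity remains defined without responders. What is missing is a planned summary with a confidence interval.
- A reader might infer that 51% and 2.4% are upper bounds on having no comparison. They are not, because a responder may lack a paired sample.
- A reader might infer that the timing passages plainly contradict each other. For biopsies, section 7.1.2.7 says cycle 4 day 1 ± 7 days and section 11.1 says after four doses ± 1 week. Dose 4 is due on cycle 4 day 1, so the windows overlap. For restaging, section 7.1.2.6 places it after "4 cycles of pembrolizumab (cycle 4; week 21-22) and after cycle 8 (week 33-34"), while study calendar note H says 12 weeks. The later weeks may be counted from the start of prior PD-1 therapy: 12 + 3·3 = 21 and 12 + 7·3 = 33. That is an inference. The clock needs stating, but a conflict is not established.

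**Conclusion.** The concern holds. The stated method tests association with response, while the objective and hypothesis ask about change in treated patients, and no section supplied plans an estimate of that change. A change common to all patients would be detected only at the test's error rate. Without a responder who has paired samples, the planned comparison cannot be made.

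The binomial figures rest only on the plan's rule and response rates. The SD-scale figures rest on the assumed alpha and normality. The 1 SD and 1.5 SD effects are illustrative.

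The gap is in prespecification, not in data collection. The same samples could be summarised later, but the summary and its time point would then be chosen after serial data had been seen.

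**What to change.** In section 8.5.3, keep the responder contrast and add a within-patient estimate of change from screening, with a 95% CI, in all treated patients with paired samples. In detail:
- Name one post-treatment time point no later than the first restaging. After that, continuation depends largely on disease status or judged clinical benefit (sections 5.2.2, 5.8 and 7.1.5.3), so later samples come from a selected group.
- When naming it, clarify the biopsy wording in sections 7.1.2.7 and 11.1, and state the clock for first restaging in section 7.1.2.6 and study calendar note H.
- Report the number of missing pairs with reasons, including patients who leave before first restaging.
- Present the results as descriptive estimates, not as a second family of confirmatory tests across the flow cytometry, repertoire and sequencing measures.
- Word them as change after FMT plus pembrolizumab.

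The cost is SAP wording, a little more analysis work and the timing clarification. No new samples are needed. The limitation remains that one arm cannot separate FMT from pembrolizumab, the high-fiber diet or time.
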